6.8 Missing Data

See [Section 6.5](#) for methods for handling missing data for primary and secondary efficacy endpoints. Missing data will not be imputed for safety analyses except for the purpose of identification of TEAEs and prior or concomitant medications with missing start or end date. Imputation rules for the partial or missing dates will be pre-specified in a separate document. All available data will be presented on the data listings as collected (no imputation).

6.9 Analyses Related to COVID-19

This section describes the pre-specified analyses to assess the potential impact of the COVID-19 pandemic on the study conduct and the evaluation of efficacy and safety of the drug.

Two populations defined:

COVID-19 impacted: Any patients with important protocol deviations due to COVID-19 including missed important visits, missed data and changes in methods of important assessments or those who are infected with COVID-19

COVID-19 infected: any patient with a reported infection (a subgroup of COVID-19 impacted)

6.9.1 General

Important protocol deviations due to COVID-19 including missed important visits, missed data and changes in methods of important assessments will be summarized by treatment groups.

Number and percent of patients who are COVID-19 infected and impacted will be summarized by treatment groups. The demographic and baseline disease characteristics and extent of exposure to study drug will be summarized for these patients.

Potential additional analyses with COVID-19 infected and COVID-19 impacted may be done for any of the endpoints including patient reported outcomes etc.

Listing of all patients that are COVID-19 impacted and infected will be reported.

6.9.2 Efficacy

6.9.2.1 Progression Free Survival

Two kinds of events due to COVID-19 can impact the PFS endpoint: deaths and missing tumor assessments.

The first one is missing tumor assessment due to COVID-19 (COVID-19 impacted). Since primary analysis will handle missing tumor assessment due to cause including COVID-19 (described in [Table 4](#)), this scenario is covered by the primary analysis missing tumor assessment handling.

The second one is if there are a total of 10 or more patients who die due to COVID-19 (COVID-19 infected) without a documented disease progression or starting a new anti-cancer therapy or missing at least 2 consecutive scheduled radiographic disease assessments for reasons not related to COVID-19, the following sensitivity analyses will be performed:

- a. These patient will be considered as censored at the date of death due to COVID-19. The primary analyses described in section 6.5.1 (log-rank test and Cox proportional hazard model) will be repeated using this adjusted censoring rule.

- b. Inverse probability of censoring weighting (IPCW) approach will be used to adjust for potential bias of the planned primary analysis introduced by COVID-19 death. With this approach, COVID-19 death will be modeled using a Cox model with treatment group and factors specified in section 6.5.3.7 as covariates. Hazard for COVID-19 death will be estimated for each subject based on which weights will be obtained. The analyses described in section 6.5.1 (Cox regression model and KM estimates) will be performed using these weights.

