4.2 Determination of Sample Size

The study anticipated approximately 416 patients, with 1:1 for CB-Cabo vs. Pbo-Cabo, and is anticipated to provide sufficient efficacy data to demonstrate a clinically and statistically significant benefit for telaglenastat for the primary endpoint of PFS per IRC.

[figure not shown]
For the purposes of study design, it is assumed that the control arm's true median PFS will be approximately 8 months based upon recently published randomized Phase 3 study results with cabozantinib monotherapy (Choueiri 2015), and that the assumed true hazard ratio (HR) favoring CB-Cabo over Pbo-Cabo will be 0.69, corresponding to an increase of 3.6 months from 8 months to 11.6 months.

The proposed study enrolled patients with an accrual period of 16 months and additional follow-up of at least 8 months. With the control arm's median PFS being 8 months and the true PFS HR of experimental patients to control patients is 0.69, the study will require approximately 262 PFS events in order to reject the null hypothesis of equal PFS between the two treatment arms with a power of 0.85. This estimation assumes a 2-sided type I error rate of 0.05, uniform accrual, exponential PFS distributions and the log-rank test for PFS comparison. The estimate of the number of events required to demonstrate efficacy with regard to PFS is shown in [Table 2](#).

To control the overall type I error rate for treatment comparisons at 2-sided test at 0.05, when PFS per IRC is statistically positive, all of the α will be passed to the secondary endpoint of OS, which will be tested at a 2-sided α level of 0.05 (see Figure 2).

OS will be tested using the group sequential method at the interim (when PFS is assessed as described above) and final analyses based on the 2-sided α level of 0.05. Statistical significance at the interim analysis of OS will be tested as described in Table 3, which also shows estimated number of OS events. The stopping boundaries for the interim and final OS analyses will be calculated using the Lan-DeMets approximation to the O'Brien-Fleming boundary. Table 3

Figure 2: Progression-Free Survival and Overall Survival Analysis Testing Strategy, Alpha Allocation

IRC, independent radiology committee; OS, overall survival; PFS, progression-free survival.

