- 1) demographics (age [<75 vs ≥ 75], sex [F vs M], and race/ethnicity)
- 2) baseline prognostic characteristics (KPS performance status [70-80, 90-100], IMDC prognostic risk grouping [EDC version], number of organs with metastases [1, 2, ≥ 3], prior nephrectomy, and prior radiotherapy, time from metastatic diagnosis [>1 and ≤ 1 year])
- 3) Prior therapies (previous anti-angiogenic therapies [yes/no], number of prior TKI [1, 2, ≥ 3], prior PD-1/PD-L1 [yes, no], prior nivo/ipi [yes, no], number of prior line of therapy [2, 3])
- 4) Metastatic Sites (lung, lymph node, bone, liver, brain, other as categories)

5) Geographic region (US/ex US)

Summaries of PFS and OS, including unstratified HRs estimated from Cox proportional hazards models and Kaplan-Meier estimates of median PFS and OS, will be produced separately for each level of the categorical variables for the comparisons between treatment arms and displayed in a forest plot (Lewis 2001).

Summaries of ORR by subgroup defined above will also be provided.

Analyses of subgroups with sample size too small may not be performed.

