6.9.2.2 Overall Survival

If there are a total of 10 or more patients who die due to COVID-19, similar sensitivity analyses described for the PFS (a and b) above will be performed for the OS endpoint.

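### The COVID-19 censoring-weight model enters about 25 terms for as few as 10 deaths, from a subgroup list that does not work as a joint covariate set

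*SAP*

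**What the plan says.** SAP 6.9.2.1 provides two sensitivity analyses for PFS. Both are triggered when at least 10 patients die of COVID-19 without earlier documented progression, new anticancer therapy, or two consecutive scans missed for reasons unrelated to COVID-19. Item (a) censors these patients at death and repeats the log-rank and Cox analyses. Item (b) uses inverse-probability-of-censoring weights, for which "COVID-19 death will be modeled using a Cox model with treatment group and factors specified in section 6.5.3.7 as covariates". For OS, SAP 6.9.2.2 applies its own trigger of 10 COVID-19 deaths, after which "similar sensitivity analyses described for the PFS (a and b) above will be performed for the OS endpoint".

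The factors are those of SAP 6.5.3.7 (Subgroup Analyses), a forest-plot list in five groups: demographics, baseline prognosis (including "prior nephrectomy, and prior radiotherapy, time from metastatic diagnosis"), prior therapies, metastatic sites and region.

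For this model the SAP states no variable selection, pooling of sparse levels, penalization, weight stabilization or truncation, variance method or time axis. It does have sparsity rules elsewhere. SAP 6.5.1 drops stratification factors when a cell has fewer than 10 PFS events, and SAP 6.5.3.7 allows small subgroups to be skipped. Neither rule is carried over to the weight model.

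**The concern.** A subgroup list is used one factor at a time, so gaps and overlaps in its coding do little harm. A regression uses all factors together. With more terms than deaths, some factor levels will contain no deaths or all of them. Their coefficients then have no finite maximum-likelihood value, and the fitted hazards follow chance patterns. The weights inherit that noise.

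Item (b) is the analysis meant to adjust PFS and OS for covariate-dependent COVID-19 death. If its model is overfitted, and some patients have no valid covariate value, it cannot do that. The repairs would then be chosen after the data are seen.

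**Working it through.** **Design inputs (SAP 4.2).** "The study anticipated approximately 416 patients, with 1:1 for CB-Cabo vs. Pbo-Cabo", a hazard ratio of 0.69, and "the study will require approximately 262 PFS events in order to reject the null hypothesis" with power 0.85 at 2-sided 0.05. The SAP gives no operating figure for the weight model, so the event count is the nearest stated figure to reproduce.
- Schoenfeld: 4 × (1.960 + 1.036)² / (ln 0.69)² = 35.91 / 0.1377 = 260.8, so 261 events. Power at 262 events is 0.852.
- Expected events with 416 patients, exponential PFS and uniform accrual: 262.2 at 15 + 7 months (protocol 14.8) and 276.7 at 16 + 8 months (SAP 4.2).

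The stated 262 reproduces.

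**Term count (SAP 6.5.3.7).**

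| Group | Terms |
|---|---|
| Treatment | 1 |
| Age, sex, race/ethnicity (taken as binary) | 3 |
| KPS 1, IMDC 2, number of organs 2 | 5 |
| Nephrectomy, radiotherapy, time from metastatic diagnosis | 3 |
| Anti-angiogenic 1, number of TKIs 2, PD-1/PD-L1 1, nivo/ipi 1, lines 1 | 6 |
| Metastatic sites | 6 |
| Region | 1 |
| Total | 25 |

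The total is 24 if sites are coded as one factor (5 terms), and more than 25 if race/ethnicity has several levels. At the trigger, 10 / 25 = 0.4 deaths per term.

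**Coding of the list, set beside other sections.**
- Prior TKIs are coded 1, 2 or ≥3. Protocol inclusion 2f admits patients whose only prior regimen is nivolumab + ipilimumab, and SAP 6.5.1 itself uses 0 vs. ≥1. Zero-TKI patients therefore have no level. With at most two counted prior lines, the ≥3 level should be nearly empty.
- Prior lines are coded 2 or 3. Inclusion 2f allows one or two, and SAP 6.5.1 uses 1 vs. 2. Perhaps the current line was meant, but read literally, one-line patients have no level.
- Nivo/ipi implies prior PD-1. Under inclusion 2f, no prior anti-angiogenic therapy implies nivo/ipi.
- The IMDC score (protocol Attachment 3) already contains KPS and a time-to-systemic-therapy item. It overlaps the separate KPS and time terms.

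**Does the Cox model have a finite maximum?** Trials of 416 patients were simulated with no true covariate effects and risk sets on time from randomization. Linear programming tested whether the partial likelihood is monotone. There were 200 replicates per cell up to 30 deaths, 100 above that, and 150 in the reduced-list column. Baseline prevalences are not in the documents and are assumed, as are a 25-month cutoff and COVID-19 deaths in months 12-25.

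| Deaths | All factors evenly split | Skewed, rarest levels removed (21-24 terms) | Skewed, 25 terms |
|---|---|---|---|
| 10 | 22% | 79-94% | 98.5% |
| 15 | 2% | 37-73% | 90.5% |
| 20 | 0% | 11-49% | 75.5% |
| 30 | 0% | not run | 51% |
| 50 | 0% | not run | 25% |
| 80 | 0% | not run | 10% |

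Entries are the share of trials with no finite estimate.

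**Weights.** Each weight is the exponential of the patient's fitted cumulative COVID-19 hazard. In 60 skewed trials with 10 deaths, 93% had a coefficient of at least 10 in absolute value. The median largest weight was 1.99 (90th percentile 2.55), against 1.07 with no covariates. No covariate had a true effect, so the extra spread is noise. Two further simulations with their own assumed prevalences gave median largest weights of 2.0 against 1.45, and 1.9 against 1.2, for the full list against three terms. In the latter, the weighted hazard ratio moved by about 0.4% in the median and at most about 3% at 10-25 deaths.

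**Calendar time.** Share of PFS at-risk time before COVID-19, assuming 16-month accrual, a 25-month cutoff and a common median of 9.5 months: 10% if COVID-19 starts at month 6, 36% at month 12 and 71% at month 18.

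**The case against.** The strongest reply is that little depends on this model. It is one of two sensitivity analyses and runs only if at least 10 qualifying deaths occur. Diverging coefficients are not reported; only the weights are used, and these stay finite and modest. That stands, and it sets the severity.

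Four stronger readings are tempting and do not hold.
- *The model is on the wrong time scale.* The SAP states no time axis for it. PFS runs from randomization and the weights must be applied on that axis, so that axis is not wrong in itself. What remains is that calendar exposure is unaddressed. If it is left out, patients followed only before the pandemic are up-weighted for a risk they never had.
- *The model usually has no valid fit.* This depends on prevalences that the documents do not give and on being near the trigger, which is 10 or more rather than exactly 10.
- *The weights depend on the software's stopping rule.* In 60 simulated trials each at 10 and 14 deaths, stopping after 8 or 20 iterations moved the median largest coefficient from about 9 to about 21. At 10 deaths the largest change in any weight was 0.0002 (median) and 0.0005 (90th percentile), and it was smaller at 14. A level with no deaths tends to zero hazard and weight 1 whether its coefficient is -10 or -20.
- *No other analysis addresses COVID-19 deaths.* Item (a) does so under the same trigger, by simple censoring.

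It is also fair to say that a shorter list gives up adjustment. Such weights need covariates linked to both COVID-19 death and outcome, so a list limited to treatment, age and region would lose the prognostic factors.

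**Conclusion.** The concern holds as a minor point. The term count, the 10-death trigger, the missing safeguards and the coding gaps can all be read from the documents without any assumed prevalence. The probability of diverging coefficients does rest on assumed prevalences: 22% to about 99% at 10 deaths, falling as deaths increase. The consequence is an overfitted, noisy weight model with an incompletely specified covariate set and no stated treatment of calendar time. The expected change in the hazard ratio is small. The primary PFS test and the passing of alpha to OS are untouched.

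**What to change.** In SAP 6.9.2.1(b), replace the reference to 6.5.3.7 with a short pre-specified list: treatment, age, and one or two factors prognostic for both COVID-19 death and PFS/OS, for example region and either IMDC or KPS. Code each factor so that every patient has a level. Treatment, age, region and KPS make 4 terms (10 / 4 = 2.5 deaths per term at the trigger); with IMDC instead of KPS there are 5 (10 / 5 = 2). Deaths per term remain low, so specify a penalized fit such as Firth. Set the COVID-19 hazard to zero before a stated pandemic start date, or include calendar time. Use stabilized weights and a robust variance. Refer to the same text in 6.9.2.2.

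Separately, reconcile the TKI and prior-line categories in 6.5.3.7 with inclusion 2f and SAP 6.5.1.

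The cost is one paragraph of SAP text, written before unblinding. The downside is that fewer covariates are adjusted for.

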6.9.2.2 Overall Survival

If there are a total of 10 or more patients who die due to COVID-19, similar sensitivity analyses described for the PFS (a and b) above will be performed for the OS endpoint.

6.9.3 Safety

Treatment-emergent AEs and SAEs due to COVID-19 infection will be summarized by treatment groups, preferred terms, and severities. All AEs for subjects diagnosed with a COVID-19 infection will be summarized by treatment groups, preferred terms, severities and the relatedness to the study drug.

